## Comparison of Different Techniques on First Attempt Success in Difficult Vascular Access

### Patients

**NCT04821362**

**July 3, 2018**

### Study Protocol

This prospective, randomized controlled trial was conducted in a tertiary care emergency department of an academic hospital.

The study included patients describing difficult vascular access history (> 2 attempts on a previous visit), with no visible or palpable veins on the upper extremity, who were assessed to have a difficult procedure by the senior nurse (according to classification; easy–moderate–difficult). Patients who do not provide consent, pregnant, <18 years, and with urgent critical intervention needs were excluded.

The randomization scheme was created by the study coordinator with a simple random method. Case report forms were numbered according to the randomization scheme with an equal number for each study groups and distributed equally to the senior nurses by study coordinator. Senior nurses performed the procedure with the corresponding method by randomly and blindly pulling the case report form in a closed envelope when they encountered patients with study inclusion criteria.

The senior nurses of emergency medicine were briefed before the study started. Consent was obtained from senior nurses who wanted to participate in the study. A pretest of 10 questions with theoretical and practical content was applied to measure their basal knowledge level regarding the use of ultrasound and near-infrared light. The principles of determining the venous structures in the upper extremity in the transverse and longitudinal planes, measuring the depth of the vessel, recognizing the arterial structures, performing the procedure on the transverse and longitudinal planes on the dummy were questioned for ultrasound device. For near-infrared light, the principles

of device usage and importance of an appropriate angle were questioned.

A score  $> 80\%$  in the pretest was accepted as success by the study team. Nurses with a test result  $\leq 80\%$  were considered unsuccessful and underwent 4 h of theoretical and 4 h of practical training. During the training, emergency medicine physicians who are experienced in the use of ultrasonography, explained the procedure of vascular access with a single operator method in the transverse and longitudinal planes. In theoretical training, ultrasonography device introduction, principles of use, linear probes and features, horizontal and longitudinal planes concepts, determination principles of venous structures, differentiation of veins from artery and nerve structures, antisepsis techniques, and case report form documentation were explained. For the nearinfrared light device, the introduction of the device, principles of use, distance between the light and area to be treated, and how the device should be positioned were explained. In practical training, ultrasonographic recognition of the normal venous structures of the upper limb on live models, target vein diameter, skin depth measurement, tracing of the target vein, gain settings, and arterial–vein separation were provided. Besides, it was ensured that each nurse performed at least three procedures on horizontal and longitudinal axes ultrasonographically on the forearm mannequin. In the practical training of the near-infrared light device, adjusting the device distance, positioning the device perpendicular to the area to be treated, identifying the vascular structures while the device was operating were shown.

A post-test that includes the same questionnaire in the pretest was applied to all nurses after theoretical and practical training, and nurses who achieved  $\geq 80\%$  were included in the study. Based on the literature data, each nurse was allowed to obtain vascular access 10 times under the supervision of the emergency medicine physician before starting the patient recruitment for research.

Sono Site Edge (FUJIFILM Sonosite, Inc.) was used for ultrasonographic procedures, and AccuVein AV 400 (AccuVein Inc.) was used for procedures using near-infrared light.

The first attempt success for peripheral intravenous catheterization is approximately 50%. To increase this success to 70%, the number of patients to be taken for each group with 0.05 type 1 error and 0.80 statistical power was 88. The study population was composed of 90 patients in each group, and 270 patients were planned.

Ethical consent was obtained from the patients before starting the research. To establish a standard approach between the procedures, 18-gauge and 20-gauge catheters were used for the arm and forearm regions, and other regions, respectively. The procedure time was started at the application of the tourniquet by senior nurse. The time was stopped when at least 5 ml of blood was obtained after venipuncture, or at least 5 ml of saline was administered successfully, and the practitioner terminated the procedure. When two attempts were unsuccessful, the third and subsequent attempts were considered as rescue interventions, and these interventions were left to the discretion of the practitioner.

For all approaches, the success of the first attempt, total procedure time, total number of attempts, need for rescue intervention were recorded by study personnels.

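### Forms are numbered to a scheme but assigned by a free pull of closed envelopes, and no described record would reveal a form that was opened, returned and used later

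*Protocol*

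**What the plan says.** Everything on this point is in the Study Protocol section of the Protocol.

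- Scheme: "The randomization scheme was created by the study coordinator with a simple random method".
- Forms: "Case report forms were numbered according to the randomization scheme with an equal number for each study groups and distributed equally to the senior nurses".
- Assignment: "Senior nurses performed the procedure with the corresponding method by randomly and blindly pulling the case report form in a closed envelope", and this is done "when they encountered patients with study inclusion criteria".
- Eligibility: patients "who were assessed to have a difficult procedure by the senior nurse". Refusal of consent is an exclusion: "Patients who do not provide consent, pregnant, <18 years, and with urgent critical intervention needs were excluded".
- Size: "The study population was composed of 90 patients in each group, and 270 patients were planned".

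Because the pull is made for patients who already meet the inclusion criteria, the difficulty rating comes before it. Consent is a condition of entry.

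The last paragraph of the Protocol lists what is recorded: first-attempt success, procedure time, number of attempts and need for rescue. Form number, draw order and draw time are not listed. The SAP contains no allocation check. Neither document describes opening in numerical order, an identifier written on the envelope before it is opened, a draw log, or a reconciliation of used and unused forms. The envelopes are called closed; sealing and opacity are not mentioned.

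**The concern.** The scheme decides how many forms of each arm exist and which number carries which arm. Once the stock is with the nurses, the link between patient and form depends on the pull alone.

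The text names one role, the senior nurse, for rating difficulty, pulling the envelope and performing a procedure whose method cannot be hidden from the operator. That person has a view of how hard the patient will be when the arm is revealed. If the arm is unwelcome, the form could go back into the stock and another be pulled.

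If nurses shared a dislike of one method and did this for patients they expected to be hard, harder patients would move to the other two arms. The disliked arm would then look better on first-attempt success, the outcome in the trial's title. If dislikes differed between nurses, the shifts would largely cancel.

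**Working it through.** **1. What would be visible under the stated procedure**

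| Event after opening | 90/90/90 totals | Form numbers | Revealed by a described check? |
|---|---|---|---|
| Form used for that patient | intact | intact | not applicable |
| Form discarded | one short | a gap | only if someone counts; no count is described |
| Form returned and used later | intact | intact | no |

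Under a free pull, form numbers are not expected to follow dates. Comparing the two afterwards therefore says nothing about the third row.

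**2. Inputs**

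From the Protocol: 90 per group, 3 × 90 = 270; first-attempt success of 50%, to be raised to 70%, a design effect of 20 points. The stated 88 per group is close to a three-group chi-square on 2 df at 50/50/70%, which gives 88.7, rounded up to 89. The usual two-sided two-group formula gives 93. This point does not depend on that figure.

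Assumed, because the documents give no value: no true effect; half the patients hard; success in hard/easy patients of 45%/55%, 40%/60% or 30%/70% (average 50%); a share r = 0.25 or 0.5 of hard patients drawn to a disliked arm is redrawn; 5, 10 or 30 nurses.

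**3. Closed form: shared dislike, one further pull, fixed totals ignored**

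A third of hard patients first draw each arm. The disliked arm keeps (1/3)(1 − r) and regains (1/3)(r)(1/3), which is (1/3)(1 − 2r/3). Each other arm has (1/3)(1 + r/3). With ph and pe the success rates in hard and easy patients:

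- disliked arm: [(1 − 2r/3)ph + pe] / (2 − 2r/3)
- each other arm: [(1 + r/3)ph + pe] / (2 + r/3)

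At 40%/60% and r = 0.5:

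- disliked: (0.6667 × 0.4 + 0.6)/1.6667 = 0.5200
- other: (1.1667 × 0.4 + 0.6)/2.1667 = 0.4923
- difference: 2.8 points

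At r = 0.25 it is 0.5091 − 0.4960 = 1.3 points. At 30%/70% the differences are 0.5182 − 0.4920 = 2.6 points and 0.5400 − 0.4846 = 5.5 points.

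**4. Simulation with totals fixed at 90/90/90**

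10,000 runs per setting, returned forms reused, nurses' shares either balanced by arm or random. The difference is the disliked arm minus the mean of the other two; rejection is the three-group chi-square at 0.05. With no redraw, rejection is 4.3–5.2%.

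Shared dislike (ranges cover the numbers of nurses and the two ways of sharing forms):

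| Hard/easy | r | One further pull: points; rejection | Always another arm: points; rejection |
|---|---|---|---|
| 45/55 | 0.25 | 0.4–0.6; 4.6–5.2% (both r) | 0.7–1.1; 4.6–5.1% |
| 45/55 | 0.5 | 0.9–1.3; as above | 1.8–2.3; 5.3–5.9% |
| 40/60 | 0.25 | 0.9–1.2; 4.8–5.2% | 1.7–2.1; 5.2–5.8% |
| 40/60 | 0.5 | 1.8–2.5; 5.2–5.8% | 3.4–4.5; 7.2–8.2% |
| 30/70 | 0.25 | 1.7–2.4; 5.2–6.5% | 3.3–4.1; 6.8–8.1% |
| 30/70 | 0.5 | 3.5–4.9; 6.9–9.3% | 6.7–8.8; 13.7–20.6% |

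Dislike varying at random by nurse: the difference is −0.1 to 0.1 points in every setting. Rejection is 4.3–6.0%, except 5.0–7.8% at 30/70 with r = 0.5 and always another arm.

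Mean redraws are 9.7–26.5 of 270; with one further pull, only 5.2–14.8 of them change the arm. The one-further-pull differences lie slightly below the closed form, as fixed totals would lead one to expect.

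**The case against.** **Concealment before opening is addressed in part.** The text describes a blind pull from closed envelopes, so the nurse is not meant to know the arm when choosing. This stands. A reader might infer that a free pull is not randomization; the documents do not support that, because a blind pull that is followed is valid. What remains is departure after opening.

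**Silence is not absence.** These are short documents. A reader might infer that no log was kept or that forms were in fact returned. Neither is stated. The supportable claim is that no such record is described.

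**The numbering does something.** It makes the stock countable, and a discarded form would leave a gap. An opened envelope might also be recognizable if it had been sealed. This stands, and it narrows the gap to forms that are returned and reused.

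**Serial order is not the only remedy.** An identifier and time written on the unopened envelope could expose a redraw even under a free pull, and serial order without dates would show little. This stands: the pre-opening record is the core. Serial opening adds that an envelope taken out of turn is visible, at almost no cost.

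**The effect is small unless assumptions are stacked.** No nurse preference or redraw rate is documented. All patients already have a difficult history, no visible or palpable veins and a rating of difficult, which makes a 30%/70% separation harder to achieve. This stands, and the larger figures should not be read as expected values.

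The objection does not point to any text that describes a pre-opening record or a check.

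**Conclusion.** The point holds as a weakness in verifiability. The scheme fixes the arm on each form, the nurse's pull fixes the patient, and a returned and reused form would not show in anything the documents describe.

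On the assumed inputs, bias is about 0 if dislikes vary by nurse. If all nurses dislike one arm and pull once more, it is about 0.4–2.5 points with false positives near 5–6% at 45%/55% or 40%/60%, against a 20-point design effect. Reaching 8.8 points and 21% needs four things together: a shared dislike, half of such draws redrawn, every redraw landing in another arm, and 30%/70% success.

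A reader might infer that the trial's result is biased. The documents do not support that, since nothing shows that any form was returned. The change is a worthwhile, inexpensive improvement. Confidence is medium, because every behavioural input is an assumption.

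**What to change.** Replace the free pull in the Protocol's randomization paragraph with this procedure:

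- Envelopes are opaque, sealed and consecutively numbered, and are opened strictly in order within each nurse's set.
- An envelope is opened only after eligibility (including the difficulty rating) and consent are recorded, and the patient identifier and time are written on the unopened envelope.
- The coordinator reconciles every number, including voided ones.

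The cost is envelope preparation and one log line per patient, with no extra patients. The nurses still hold the envelopes, so this makes departures visible but does not physically prevent them.

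The Protocol is written largely in the past tense. If enrolment is complete, the remaining step is to report the concealment limitation, because checking form numbers against dates cannot reveal redraws made under a free pull.

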Comparison of Different Techniques on First Attempt Success in Difficult Vascular Access Patients

NCT04821362

July 3, 2018

Statistical Analyses Plan:

Statistical analyses will be performed using the IBM SPSS Statistics for Windows, Version 25.0. Armonk, NY: IBM Corp. The suitability of continuous variables to normal distribution will be examined using analytical methods (Kolmogorov–Smirnov). Descriptive analysis will be performed using the median and interquartile range for non-normally distributed variables and means and standard deviations for normally distributed variables. In the comparison of independent groups, Kruskal–Wallis tests will be used for non-normally distributed data. The Mann-Whitney U test will be performed to test the significance of pairwise differences for multiple comparisons using Bonferroni correction. For categorical variables, the difference between groups will be evaluated with the Chisquare test. A p-value less than 0.05 will be considered to show a statistical result.

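### Bonferroni on the three pairwise Mann-Whitney tests is valid, but with three groups a closed procedure gives more power at the same 5% familywise error (optional change)

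*SAP*

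**What the plan says.** The SAP gives two sentences on comparing groups when data are not normal. The first is the overall test: "Kruskal–Wallis tests will be used for non-normally distributed data". The second is the pairwise rule: "The Mann-Whitney U test will be performed to test the significance of pairwise differences for multiple comparisons using Bonferroni correction". Nothing says that the pairwise tests are run, or count, only if the overall test is significant. The significance level is 0.05. Categorical outcomes go to a chi-square test, with no pairwise procedure and no correction.

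The Protocol fixes the number of groups: "The study population was composed of 90 patients in each group, and 270 patients were planned", with forms prepared "with an equal number for each study groups". Its last paragraph lists four outcomes: first-attempt success, total procedure time, total number of attempts and need for rescue. Only procedure time and number of attempts would normally reach the Mann-Whitney tests. The single power statement concerns first-attempt success, 50% against 70%, "with 0.05 type 1 error and 0.80 statistical power was 88" per group. No effect size, standard deviation or power is given for time or attempts.

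**The concern.** With exactly three groups, Bonferroni asks more of each pair than 5% familywise control requires, provided that a significant overall test is demanded first. The plan already intends to run that overall test but gives it no formal role, and pays for error control a second way by judging each pair at 0.0167.

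At stake is the chance of showing which techniques differ on procedure time and number of attempts. The loss is largest when the claim needs two pairwise results at once, for example that one technique differs from both of the others.

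**Working it through.** **Inputs.** Groups: 270 / 90 = 3 (Protocol). Pairs: 3 × 2 / 2 = 3. Bonferroni level: 0.05 / 3 = 0.0167. Tests are taken as two-sided, which the documents do not state.

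**The plan's own figure.** The stated 88 per group is for first-attempt success. The unpooled two-sided formula gives (1.96 + 0.8416)² × (0.5 × 0.5 + 0.7 × 0.3) / 0.20² = 7.849 × 0.46 / 0.04 = 90.3. The pooled formula gives 93. A three-group chi-square with rates 50/50/70 gives 89. Power at 88 is 77.8% (pooled), 79.0% (unpooled) or 78.9% (exact Pearson chi-square). So 88 is close to standard results, but it says nothing about the Mann-Whitney outcomes.

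**Why a gate suffices with three groups.** Let each null hypothesis be that two groups have the same distribution. If any two of the three equalities hold, so does the third. The only intersection hypothesis is therefore the global null, which Kruskal-Wallis tests at 0.05. Requiring Kruskal-Wallis to be significant, and then the pair's own test at 0.05, is a closed procedure. This does not carry over to four or more groups.

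**Familywise error** (simulation, 3 × 90, normal data, 100,000 runs):

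| Rule | All groups equal | Two equal, one far away |
|---|---|---|
| Pairs at 0.05, no gate | 12.4% | 5.0% |
| Pairs at 0.0167, no gate (SAP as written) | 4.4% | 1.7% |
| Pairs at 0.05, Kruskal-Wallis gate | 5.0% | 5.0% |

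If the three tests were independent, the first entry would be 1 − 0.95³ = 14.3%; they share groups, so it is lower. A smaller run of 6,000 gave 13.1%.

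**Pairwise power.** The effect has to be assumed. A shift giving 80% power for one Mann-Whitney test at 0.05 is (1.96 + 0.8416) × √(2/90) / √(3/π) = 0.427 SD. Results in per cent, gate plus 0.05 against Bonferroni without a gate:

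| Assumed single-test power | One group differs | Third group midway, extreme pair |
|---|---|---|
| 70% | 63.4 vs 52.7 (gain 10.7) | 57.4 vs 52.6 (gain 4.8) |
| 80% | 75.0 vs 64.8 (gain 10.2) | 69.0 vs 64.9 (gain 4.1) |
| 90% | 87.4 vs 79.0 (gain 8.4) | 82.4 vs 79.4 (gain 3.0) |
| 95% | 93.6 vs 88.1 (gain 5.5) | 89.9 vs 88.0 (gain 1.9) |

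In the midway case at 80%, each adjacent pair goes from about 15–16% to about 27–28%, a gain of about 12 points.

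**A second model.** Log-normal times with log-SD 0.6 and a shift of 0.25 (both assumed) correspond to 0.25 / 0.6 = 0.417 SD, almost the same effect, since rank tests ignore the log transformation. With one group shifted, separate runs give 61 to 63% under Bonferroni and 71 to 74% under the gate, again about 10 points. Holm gives 64 to 66%. Power to show both true differences is about 45 to 47% (Bonferroni), 51 to 53% (Holm) and 63 to 65% (gate). With the third group midway, the extreme pair goes from 61% to 65%, and adjacent pairs gain 10 to 11 points. Across these configurations Holm gains about 1 to 4 points per pair.

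**Ties.** Number of attempts is discrete. With attempts modelled as geometric, capped at 5, and success per attempt 50/70/70 (model assumed), pairwise power goes from 78% to 86% and power for both differences from 67% to 82%. Familywise error with equal rates is 4.6% under the gate.

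**The case against.** The strongest reply is that Bonferroni is a prespecified, valid choice. It needs no gate and has matching simultaneous confidence intervals, which the gated procedure lacks. All of that stands. The benefit also depends on what is being claimed: with one group shifted, the chance of finding at least one pairwise difference is 79% under the plan and 81% under the gate, so the gain lies mainly in showing the second difference.

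Three stronger readings are tempting, and the documents support none of them.

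- *Bonferroni is redundant and can be struck out.* A reader might infer this because Kruskal-Wallis appears just before it. The SAP never makes that test a condition, so striking out the correction would raise familywise error from 4.4% to 12 to 13%.
- *The plan loses 10 points of power.* No effect size is given for time or attempts. The figure belongs to one configuration and one range of assumed power.
- *The correction weakens the main comparison.* First-attempt success goes to chi-square, where no pairwise correction is stated, so there is no Bonferroni baseline against which to claim a gain. The real gap there is the missing pairwise rule. If 0.0167 were carried over, power for 50% against 70% at 90 per group would be 63.8% instead of 78.7%, and 80% would need 125 per group instead of 93 (pooled formula). That is a consequence of one possible choice, not of the plan as written.

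**Conclusion.** The concern holds as a point of efficiency. As written, the SAP's pairwise rule controls familywise error and invalidates no claim. With three groups, a binding Kruskal-Wallis gate achieves the same 5% control with more power. Around 80% single-test power, the gain is about 10 points per true difference when one group differs. With the third group midway it is 4 to 5 points for the extreme pair and 10 to 12 for adjacent pairs. Over 70 to 95% single-test power, the gain runs from about 11 down to about 5 points in the first case, and from about 5 down to about 2 for the extreme pair in the second.

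These sizes rest on assumed location shifts, two-sided tests and 90 patients per group; ties in number of attempts change them somewhat. The control of error does not depend on the assumed effect, only on there being three groups and on the gate being binding. Since the outcomes concerned have no stated power and the present rule is valid, the change is optional.

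**What to change.** Replace the pairwise sentence in the SAP with:

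> If the Kruskal-Wallis test is significant at 0.05, each of the three pairwise Mann-Whitney tests will be judged at 0.05 (closed testing procedure for three groups); otherwise no pairwise difference will be claimed.

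The second clause is essential: without it, the error control is lost. If the sponsor prefers no gate, replace Bonferroni with Holm, which keeps familywise control and is never less powerful than Bonferroni.

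The same gate can supply the missing rule for categorical outcomes: the 3 × 2 chi-square first, then pairwise 2 × 2 tests at 0.05. That would fill a gap, and should not be presented as a power gain over the plan.

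The cost is one sentence, with the same tests, software and data. The drawback of the gate is that no simultaneous confidence intervals match it, so ordinary 95% intervals would be reported and should be labelled as unadjusted.
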